Visit 6- Interim Visit (Month 6) (+/- 14 days) This in-person visit will include a physical exam, a discussion about any medications the participant may be taking, review of home blood glucose monitoring results, a review of adverse events, and a review of insulin usage, and blood glucose values over 3 days prior to this visit. The participant will complete a 2 hr Mixed Meal Tolerance Test and have blood drawn for a HbA1c and liver function tests. A urine sample will also be tested for pregnancy if the participant is female and of childbearing potential. Participants will be provided with a 3-month supply of the study medication. Participants will continue the study medication.

Visit 7- Interim Visit (Month 9) (+/- 14 days) This in-person visit will include a discussion about any medications participants may be taking, review of home blood glucose monitoring results, a review of adverse events, and a review of insulin usage over 3 days prior to this visit. Participants will have blood drawn for a HbA1c and liver function tests. Participants will be provided with a 3-month supply of the study drug/ placebo. Participants will continue the study medication.

Visit 8- Interim Visit (Month 12) (+/- 14 days) This visit will include a physical exam, a discussion about any medications participants may be taking, review of home blood glucose monitoring results, a review of adverse events, and a review of insulin usage and blood glucose values over 3 days prior to this visit. Participants will complete a 2 hr Mixed Meal Tolerance Test and have blood drawn for a HbA1c and liver function tests. Medication will be stopped at the end of 12 months.

Visit 9- Interim Visit (Month 15) (+/- 1 month) This phone visit will include discussion about any medications participants may be taking, review of home blood glucose monitoring results, a review of adverse events, and a review of insulin usage over 3 days prior to this visit.

This in-person visit will include a physical exam, a discussion about any medications participants may be taking, review of home blood glucose monitoring results, a

review of adverse events, and a review of insulin usage and blood glucose values over 3 days prior to this visit. Participants will complete a 2 hr Mixed Meal Tolerance Test and have blood drawn for a HbA1c and liver function tests.

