i. Endpoints: The primary endpoints will be the area under the stimulated C-peptide curve of a 2- hour mixed meal tolerance test (MMTT) conducted at screening, and during the 12 months of drug treatment at 6 and 12 months and at 6 months after drug or placebo is stopped.

The study will also examine as secondary endpoints the effect of the experimental treatment on diabetes-specific autoantibodies and metabolic parameters. Interim metabolic assessments will consist of periodic review of glucose records and reports of hypoglycemia, insulin dose and HbA1c.

- ii. Trial Design: This single-center double-masked, Phase II placebo-controlled study will examine the efficacy of TUDCA to arrest beta cell hypofunction/destruction in 20 subjects with new- onset T1D (ages 18-45 years), randomized within 100 days of diagnosis). All subjects will receive standard intensive diabetes treatment with insulin and dietary management, consistent with American Diabetes Association Standards of Care. Diabetes management will be done by the primary diabetes care team at the Berrie Center. Subjects will be randomly assigned 1:1 to receive either daily TUDCA 1750 mg/day or placebo for 12 months. All subjects will be followed for until study end and will be offered option for re-contact in the informed consent so that longer-term study follow-up is a possibility. Enrollment is expected to occur over 18 months. The mean c-peptide responses to MMTT in the TUDCA treatment group will be compared to the placebo-treated group at 0, 6, 12 and 18 months. The study will also examine the effects of TUDCA treatment on other T1D- related metabolic and immunologic outcome measures.
- iii. Exploratory outcome: If a significant change in c-peptide responses are detected in both groups, we will compare the *in vivo* responses to ER stress relief to in-vitro responses to ER stress relief. In these subjects, we will compare the clinical response to an agent that reduce ER stress to the response of the iPS-derived beta cells, derived from the same subject, when treated with the same experimental agent to reduce ER stress.

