- iv. Treatment and Dose: Subjects will be treated with either TUDCA at a dose of 1750 mg/day or placebo for 12 months with an additional 6 months of follow-up. 1750 mg is the most commonly used dose used to treat biliary disease and was used in a recent study of human obesity and insulin resistance (39). In this 4 week study, an effects on ER stress was not observed on adipose cells; however we plan a longer treatment time period and hypothesize that since TUDCA undergoes extensive

hepatic metabolism, the exposure of pancreatic beta cells to drug at this dose may be sufficient to cause an effect on ER stress. In addition, in vitro studies will enable us to manipulate exposure of beta cells to a range of TUDCA concentrations, thus revealing extent of individual differences in sensitivity to the agent.

v. Duration: All subjects will be followed for 1 year of treatment and at least 6 months of follow-up.

VI DSMB: The progress of the study will be monitored by the DSMB which will review safety data and make recommendations regarding continuation, termination, or modification of the study. Based on an 18 month enrollment period and an additional study period of at least 6 months, the DSMB will formally review the safety data, enrollment, and clinical outcome data at least twice yearly.

Vii The number of subjects who discontinue study treatment will also be included in the reports prepared for the DSMB.

Statistical analysis: These studies are pilots in which we anticipate substantial interindividual differences in responses to the proposed *in vivo* intervention (TUDCA). We will compare the clinical endpoints between treated and control subjects using repeated measures ANOVA, treating (if indicated) age, gender and BMI as covariates. The endpoints of the in vitro studies will be analyzed for differences between individuals regardless of the experimental group to which they have been randomized. These analyses will inform us of the range of autonomous beta cell differences in response to ER stress, and to the mitigation conveyed by TUDCA. These data will then be related to clinical endpoints, probing for the ability of the *in vitro* studies to predict (correlate with) clinical course and response to TUDCA. We are experienced in all of the relevant analytic techniques and have the software on hand. If necessary, we have access to expert statistical consultations through the Columbia NIH CTSA.

3. Study Procedures MMTT and skin biopsy

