 - iii. Population to be studied: New-onset T1D. We will recruit individuals between the ages of 18 and 45 with new- onset T1D (within 100 days of diagnosis). All patients will be in otherwise good health. Inclusion criteria will include: at least one diabetes- related autoantibody present (insulin autoantibody alone will not be sufficient in subjects treated with insulin for > 14 days) and a stimulated C-peptide levels > 0.2 pmol/ml measured during a mixed meal tolerance test (MMTT) conducted at least 21 days from diagnosis of diabetes and within one month (37 days) of randomization to either TUDCA or placebo. Pregnant women will be excluded. Participants of childbearing potential and/or their partners must agree to use acceptable methods of birth control beginning at the pre-study visit and throughout the study.

Examples of acceptable methods of birth control include abstinence, or 2 of the following: intrauterine device (IUD-with or without local hormone release), diaphragm, spermicides, cervical cap, contraceptive sponge, and /or condoms.

- iv. Drug handling/distribution/administration is conducted in accordance with the policies of the Research Pharmacy and Columbia University Medical Center
- 5. Study Instruments (e.g., Questionnaires, Interview Outlines, Focus Group Guides): N/A

6. Study Subjects

I. Subject Inclusion Criteria

- 1. Be between the ages of 18 and 45 years.
- 2. Be within 3 months (100 days) of diagnosis of T1D based on ADA criteria.
- 3. Must have at least one diabetes-related autoantibody present.
- 4. Must have stimulated C-peptide levels > 0.2 pmol/ml measured during an MMTT conducted at least 21 days from diagnosis of diabetes and within one month (37 days) of randomization.
- 5. If participant is female with reproductive potential, she must be willing to avoid pregnancy and have a negative pregnancy test during the 12 months of treatment and for an additional 3 months.
- 6. Must be willing to comply with intensive diabetes management.
- 7. Must be willing to undergo 3 mm skin biopsy at randomization.

II. Subject Exclusion Criteria

- 1. Be currently pregnant, lactating or anticipating getting pregnant.
- 2. Ongoing use of medications known to influence glucose tolerance.
- 3. Have serologic evidence of current or past HIV, hepatitis B, or C infection.

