- 4. Have any complicating medical issues or abnormal clinical laboratory results including abnormal liver function test (more than 1.5 x ULN) that interfere with study conduct or cause increased risk.
- 5. Have a history of malignancy.
- 6. Currently using non-insulin drugs that affect glucose control.
- 7. Currently using drugs that may interfere with TUDCA absorption or effect such as bile acid sequestering agents (cholestyramine and colestipol), aluminum based antacids, estrogens, oral contraceptives and clofibrate.
- 8. Currently participating in another T1D treatment trial or Sensitivity to TUDCA or other similar agent.
- iii.Subject withdrawal criteria: An intent—to-treat approach will be used. Subjects will not be replaced. All data acquired prior to termination for the reasons outlined below will be included in the primary analysis unless a participant withdraws consent. Every effort will be made to conduct a final study visit with the participant and participants will be followed clinically until, if applicable, all adverse events resolve. All subjects will be offered clinical follow-up at the Berrie Center for T1D.

Reasons for withdrawal and stopping rules: The drug will be stopped by the investigator because of serious and unexpected adverse events, safety laboratory parameters and/or vital signs. Subject may be withdrawn by the investigator; the subject my withdraw from the study; there may be an Intercurrent illness or event that precludes further to the study site or ability to evaluate disease.

Treatment of Subjects: Participants will be treated with either TUDCA at a dose of 1750 mg/day or placebo for 12 months, with study visits every 3 months during treatment, and undergo at least 6 months of follow-up, depending upon time of randomization. The study will be stopped based on occurrence of serious and unexpected adverse events, safety laboratory parameters and/or abnormal vital signs. Subjects will agree to avoid the following drugs during the study: non-insulin drugs that affect glucose control, bile acid sequestering agents (cholestyramine and colestipol), aluminum based antacids, estrogens, oral contraceptives and clofibrate. Subjects will be offered option of ongoing clinical care at Berrie Center for T1D as well as option for re-contact in informed consent, providing possibility for longer-term follow-up studies to be performed in the future on these subjects.

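### Repeated measures ANOVA is named without a test contrast, a missed-visit rule or screening C-peptide as a covariate; a baseline-adjusted mixed model on all available data would be a better analysis at almost no cost

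*Combined protocol and SAP*

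**What the plan says.** - **Model.** The Statistical analysis paragraph of Section 2 compares the arms "using repeated measures ANOVA, treating (if indicated) age, gender and BMI as covariates". It names no test (group main effect, group-by-time interaction or a single visit) and gives no rule for a missed visit.
- **Outcome.** Section 2.i puts the screening mixed meal tolerance test (MMTT) inside the primary endpoint, with those at months 6 and 12 and "at 6 months after drug or placebo is stopped". Section 2.ii lists month 0 among the times at which the arms are compared.
- **Screening value.** Every participant has one, because inclusion criterion 4 in Section 6 reads: "Must have stimulated C-peptide levels > 0.2 pmol/ml measured during an MMTT conducted at least 21 days from diagnosis of diabetes".
- **Analysis principle.** Section 6.iii says that an intent-to-treat "approach will be used. Subjects will not be replaced". It continues: "All data acquired prior to termination for the reasons outlined below will be included in the primary analysis unless a participant withdraws consent".
- **Reasons for withdrawal.** The list that follows includes: "Subject may be withdrawn by the investigator; the subject my withdraw from the study". It does not separate leaving the study from withdrawing consent.

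**The concern.** The model's name leaves two decisions open, and each could be made after the data are seen.

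The first is the contrast. The month-0 value precedes treatment, so it carries no treatment effect. A group main effect averaged over all four visits is therefore diluted, while a change-from-month-0 contrast is not. Neither uses the screening value as efficiently as a covariate does.

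The second is the missed visit. The classical form of repeated measures ANOVA needs complete rows, so it would delete anyone who lacks one of the three post-baseline MMTTs. That would contradict the Section 6.iii rule that data gathered before termination are analysed. With 20 participants randomised 1:1 and no replacement, one participant is about 10% of an arm.

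A smaller, separate matter is the consent exception. Read literally, it takes C-peptide values already collected from a randomised participant out of an intent-to-treat analysis.

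**Working it through.** **The plan's own figure.** The sample size of 20 comes without alpha, power, effect size, SD, dropout rate or correlation. It can be neither reproduced nor called wrong.

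**Inputs.** From the documents: 20 participants, 1:1 (10 per arm), MMTTs at months 0, 6, 12 and 18. Assumed: two-sided 5%, unit SD at each visit, equal correlation r between visits, and for power a 1 SD effect at every post-baseline visit. Month 18 is included in that effect although treatment ends at month 12, and Section 3 treats persistence only as possible. Power uses the noncentral t distribution.

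**1. Group main effect against adjusted post-baseline mean.**
- Main effect over four visits: effect 0.75 SD, variance (1+3r)/4, 18 df.
- Post-baseline mean, unadjusted: effect 1 SD, variance (1+2r)/3, 18 df.
- Post-baseline mean adjusted for screening AUC: effect 1 SD, variance [(1+2r)/3 − r²] × (1+1/16), 17 df. The last factor is the cost of estimating the slope.

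At r = 0.5 the main effect has variance 0.625 and noncentrality 0.75/√(0.625 × 2/10) = 2.12. The adjusted mean has variance 0.4167 × 1.0625 = 0.443 and noncentrality 1/√(0.443 × 2/10) = 3.36.

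| r | Main effect, months 0–18 | Post-baseline mean, unadjusted | Post-baseline mean, adjusted |
|---|---|---|---|
| 0.3 | 63% | 82% | 87% |
| 0.5 | 52% | 74% | 89% |
| 0.7 | 44% | 66% | 96% |
| 0.8 | 41% | 62% | 99% |

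The first step across the table is the dilution by month 0. The second is the value of the covariate.

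**2. Change from month 0 against covariate adjustment, month 12, 80% power.** Variance factors are 1 (month 12 alone), 2(1−r) (change) and (1−r²)(1+1/16) (adjusted).

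| r | Month 12 alone | Change from month 0 | Adjusted | Gain over change |
|---|---|---|---|---|
| 0.5 | 1.325 SD | 1.325 SD | 1.187 SD | 1 − 1.187/1.325 = 10% |
| 0.8 | 1.325 SD | 0.838 SD | 0.822 SD | 1 − 0.822/0.838 = 2% |

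**3. Precision cost of deleting incomplete rows.** This is the month-12 variance relative to complete data, given baseline. The correlation between post-baseline visits is then (r−r²)/(1−r²) = 0.333 at r = 0.5 and 0.444 at r = 0.8. The missingness rates are assumed.
- Total dropout D of 5% or 10%, split evenly before months 6, 12 and 18. Deletion gives 1/(1−D) = 1.053 or 1.111. The mixed model gives 1.031–1.033 or 1.064–1.067. The standard error ratio is 1.010 or 1.020–1.022, a cost of 1–2%.
- Independent misses q of 5% or 10% per visit. Deletion gives 1/(1−q)³ = 1.166 or 1.372. The mixed model gives 1.039–1.044 or 1.083–1.094. The standard error ratio is 1.057–1.060 or 1.120–1.126, a cost of 6–13%.

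**4. Bias from deletion depends on the contrast.** Suppose the one or two participants in an arm with the lowest month-6 values are deleted. The expected two lowest of 10 standard normals are −1.539 and −1.001.
- Change to month 12: Cov(Y12 − Y0, Y6) = r − r = 0, so there is no shift.
- Main effect over four visits: (1+3r)/4 × 1.539/9 = 0.11 to 0.15 SD for one, and (1+3r)/4 × 2.540/8 = 0.20 to 0.27 SD for two (r = 0.5 to 0.8).

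**5. Consent exception.** Removing one of 10 shifts that arm's mean by 0 if unrelated to outcome. The shift is 0.739/9 = 0.08 SD if the person comes from the lower half, and 1.539/9 = 0.17 SD if it is the lowest value. Against the standard error of the arm difference, √(2/10) = 0.447 SD, the last two are 0.18 and 0.38 standard errors.

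**The case against.** The strongest reply is that baseline is already in the analysis. Month 0 is a level of the repeated outcome, so a group-by-time contrast measures change from screening. That stands. A reader might infer that the plan ignores baseline C-peptide, and Sections 2.i and 2.ii do not support this. Against a change contrast the covariate gains only 10% to 2% in detectable difference.

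A reader might also infer that the plan deletes incomplete cases and is biased as a result. The documents do not support that either. No deletion rule is written, and Section 6.iii points towards using all available data. A month-12 comparison that ignored baseline would shift by 0.09 to 0.25 SD when the lowest month-6 values are lost, but the change contrast would not shift. If missingness depends on the unseen month-12 value, the change contrast with deletion shifts by 0.03 to 0.16 SD and the mixed model by 0.05 to 0.21 SD. So no bias advantage at month 12 can be claimed over a change contrast.

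On consent, the exception may only mirror the consent form, which is not in the text available, or may mean that no new data are collected. A firm charge that intent-to-treat is breached goes too far. The plan also promises: "Every effort will be made to conduct a final study visit with the participant".

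Finally, this is a self-described pilot that anticipates a trend and claims no power. That lowers the stakes, but it does not answer the question of which contrast will be tested.

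**Conclusion.** The point holds as a better available method, together with an unnamed contrast. It is not a numerical error. The size depends on which test was meant: large if it is the group main effect including month 0 (63–41% power against 87–99%), modest if it is change from month 0 (1.32 to 1.19 SD at r = 0.5, 0.84 to 0.82 SD at r = 0.8). Deleting incomplete rows, if it were done, would cost 1–2% in standard error under 5–10% dropout and 6–13% under 5–10% independent misses per visit. All of these figures rest on equal visit correlations and on effect sizes and missingness rates that the documents do not give. The consent exception is secondary and turns on a form not seen here. Severity: minor to should-fix.

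**What to change.** 1. In the Statistical analysis paragraph of Section 2, replace repeated measures ANOVA by a REML mixed model fitted to all available month 6, 12 and 18 MMTTs. Include arm, visit, arm-by-visit and screening C-peptide AUC as a covariate, with Kenward-Roger or Satterthwaite degrees of freedom. State that no participant is deleted for a missed visit.
2. Name the arm contrast that is the primary test (for example month 12, or the mean of the post-baseline visits) before data are unmasked.
3. In Section 6.iii, state that C-peptide data collected before a withdrawal of consent stay in the primary analysis, in the assigned arm, where the consent form permits. Say how this differs from leaving the study.

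Cost: changes of wording and slightly more analysis work, with no extra visits or participants. The model assumes data missing at random. With 20 participants only a simple covariance structure is practical, and it may fit imperfectly because month 18 is off treatment: "Medication will be stopped at the end of 12 months".
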